## **Section 7.0 Assessment of Efficacy**

The primary efficacy population will include patients who had baseline mean UFC levels 1.5x above the upper normal range, and who completed the 4-cycle, 4-week treatment period with no more than 2 weeks of interrupted drug doses. Baseline UFC levels are defined as the mean of three 24-hour urine specimens collected within one week of baseline visit.

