### Study Design:

- Phase II, proof-of-concept, open-label and single arm study to assess the safety and efficacy of seliciclib in patients with Cushing disease
- Rationale for study design: due to the rarity of Cushing disease in the general population, it is difficult to do a randomized placebo controlled trial with sufficient sample size numbers to achieve adequate power. By using the subjects as their own controls, we alleviate the issues with recruitment. This is a safety and activity trial to look for a sufficient effect of the drug on normalizing urinary free cortisol before proceeding to a larger, randomized placebo controlled trial.

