- Patients who were receiving mitotane and/or long-acting somatostatin analogs (octreotide LAR or lanreotide)
- Patients who were receiving pasireotide or ketoconazole before study entry must complete a 2 week washout period prior to receiving seliciclib
- Patients who have received pituitary irradiation within the last 5 years prior to the baseline visit
- Patients who have been treated with radionuclide at any time prior to study entry
- Patients with known hypersensitivity to seliciclib
- Patients with a history of non-compliance to medical regimens or who are considered potentially unreliable or will be unable to complete the entire study
- Patients with presence of Hepatitis B surface antigen (HbsAg)
- Patients with presence of Hepatitis C antibody test (anti-HCV)

*Withdrawal of Subjects:*

- Monitoring for adverse effects: Patients will be evaluated for adverse effects weekly with physical examinations, chemistry and hematology panels. Adverse events will be graded by the NCI-CTCAE and include: fatigue, fever, nausea, vomiting, anorexia, hepatic dysfunction (increased ALT/SGPT, AST/SGOT and AP), hypokalemia, hyponatremia and insomnia [IND No. 71,011-CYC202(R-roscovitine or Seliciclib)]. Seliciclib will be discontinued in those who developed worsening of visual fields, and those with toxicity greater than or equal to Grade 4 on the NCI-CTCAE. Demonstration of compromised visual fields at any time will lead to withdrawal from the study and surgical referral.

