### ***Dose delays and dose reductions:***

- Dose delay or reduction for drug-related toxicity is permitted; however the DSMB will be consulted prior to implementing any change in dosing. Dose delay or reduction will only be implemented when all supportive care measures have been exhausted without an improvement of patient status.
- Those subjects with toxicity less than or equal to NCI-CTCAE Grade 2 will continue their full dose, unless the investigator, based on clinical judgment, feels it is necessary to have their dose reduced or held.
- Patients experiencing unacceptable toxicity (Grade 3 or higher) that the investigator considers directly attributable to R-roscovitine should have their dose held, reduced, or should be withdrawn from the study (**Table 2 and 3**).
- Treatment may be delayed, up to 2 weeks, until the patient recovers completely or the adverse event reverts to Grade 1 or to baseline grade.
- A maximum two dose reductions are permitted per subject and subjects will not be re-challenged to a higher dose level.
- The Investigator will consult the DSMB prior to continuing therapy for any subject requiring a delay of more than 2 weeks for unresolved toxicity, but in general, such subjects should be withdrawn from the study.

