**Table 4. Liver Chemistry Stopping Criteria**

Hepatic AE	Management/Next Dose for R-roscoxitine

 
• ALT or AST <math>>3 \times</math> ULN and <math><5 \times</math> ULN and total bilirubin <math>\leq 2 \times</math> ULN, without signs or symptoms of hepatitis or hypersensitivity, and who can be monitored weekly
 
	
 
• Hold IP for maximum 2 weeks, repeat liver chemistry testing weekly
 
• Discuss with DSMB for possible re-challenge with IP and define dose reduction
 
• If the treatment is exhibiting efficacy and the subject wants to continue after being informed of the liver chemistry results, then the IP may be re-started at the DSMB defined dose reduction.
 
• Liver chemistries and aforementioned signs and symptoms should be monitored at a minimum of every week until resolution, stabilization, or a return to baseline values, at which point monitoring should be continued per protocol.
 

 
• ALT or AST <math>>8 \times</math> ULN; or
 
• ALT or AST <math>>5 \times</math> ULN persisting for <math>\geq 2</math> weeks; or
 
• ALT or AST <math>>3 \times</math> ULN and (total bilirubin <math>>2.0 \times</math> ULN or INR <math>>1.5</math>); or
 
• ALT or AST <math>>3 \times</math> ULN with signs or symptoms of hepatitis or hypersensitivity*
 
	
 
• Immediately and permanently discontinue IP;
 
• Complete the SAE data collection tool, the liver event CRF, and the liver imaging and/or liver biopsy CRFs, if these tests are performed;
 
• In addition to the liver event follow up assessments defined below, the following are suggested: specialist or hepatology consultation; anti-nuclear antibody, anti-smooth muscle antibody, and Type 1 anti-liver kidney microsomal antibodies; and liver imaging and/or liver biopsy to evaluate liver disease;
 
• Promptly report the event to Cyclacel within 24 hours of learning its occurrence
 
• Monitor every week until liver chemistries resolve, stabilize or return to within baseline values;
 
• Do not re-challenge with investigational product.
 

Hepatic AE	Management/Next Dose for R-roscoxitine
• If ALT or AST>3 and < 5 × ULN for > 4 weeks	Discontinue study drug

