### **Glucose metabolism adverse events**

The principal investigator is to evaluate the risks for hyperglycemia in all patients, following established guidelines by the American Diabetes Association (ADA) and European Association for the Study of Diabetes (EASD). The principal investigator is to educate the patient on the signs and symptoms of hyperglycemia.

Patients with a prior history or new diagnosis of impaired fasting glucose, impaired glucose tolerance or diabetes mellitus, or at risk of developing these conditions should monitor their blood glucose by fingerstick twice daily (fasting and 2-hours post-prandial). The patients will be encouraged to keep a diary for their blood glucose for appropriate management of the disease throughout the trial and present the collected data to their physician/diabetes specialist for evaluation.

Any patient showing a fasting plasma glucose  $> 130$  mg/dL (7.2 mmol/L), or 2-hour post-prandial capillary glucose (PPG)  $\geq 180$  mg/dL (10 mmol/L) on two consecutive measurements that are approximately 14 days apart, and/or HbA1c  $> 7\%$  is evaluated by a diabetes specialist for appropriate treatment. In addition, these patients are given information regarding diabetes disease management. Initiation or adjustment of hypoglycemic treatment is considered as early as possible at the discretion of the diabetes specialist. The above instructions regarding glucose monitoring by fingerstick and collection of blood level in a diary are given to the patients.

Patients who develop symptoms of diabetes mellitus out of control and/or fasting blood glucose values consistently as high as or above 240 mg/dL in spite of appropriate therapeutic interventions are discontinued from the study, as are those patients whose HbA1c is greater than or equal to 8% in spite of appropriate therapeutic intervention.

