### **Electrolyte metabolism adverse events**

High levels of cortisol also exert mineralcorticoid (aldosterone) activity, stimulating absorption of sodium and excretion of potassium at the renal collecting tubules. Hypokalemia is most often associated with Cushing's syndrome due to ectopic ACTH production. Patients with pituitary corticotroph tumors may present with mild hypokalemia (3.0-3.5 mmol/L). Hypokalemia associated with seliciclib appeared to be dose dependent, occurring only in doses higher than 1200 mg b.i.d. 3 days per every 2 weeks. Patients who develop serum potassium values consistently  $<3.0$  mmol/L in spite of appropriate therapeutic interventions are discontinued from the study.

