### **Section 9.0 Statistics**

Due to the rarity of Cushing disease in the general population, it is difficult to do a randomized placebo controlled trial with sufficient sample size numbers to achieve adequate power. By using subjects as their own controls, we measure pre- and post-treatment changes on the same population, therefore alleviate the issues with recruitment.

We used a Simon exact single-stage phase II design (8) to determine the sample size for 80% power and a one-sided 0.05 significance level. The trial tests the null hypothesis that the seliciclib (response rate)  $\leq 5\%$  (unacceptable response rate) versus the alternative hypothesis that  $RR \geq 25\%$  (promising response rate). We enroll 16 patients. If at least 3 of the 16 respond, we conclude that seliciclib is promising in the treatment of ACTH-producing pituitary tumors.

A regression model will be used to investigate the relationship between end-of-study UFC and baseline UFC. The comparison between serum cortisol or plasma ACTH in patients who responded to seliciclib and in those who did not respond will be performed by a Student's *t* test. Categorical variables, i.e. normalization of 24 hour UFC, development of new pituitary deficits, and visual field deficits will be compared in the pre- and post- treatment time points using fisher's exact test.

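### The decision rule counts responders among all 16 enrolled, but the primary efficacy population is completers only, and a missing end-of-treatment UFC has no stated status

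*Combined protocol and SAP*

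**What the plan says.** Section 9.0 (Statistics) describes an exact single-stage design: unacceptable response rate 5%, promising rate 25%, one-sided 0.05, 80% power, 16 enrolled. Its rule is: "If at least 3 of the 16 respond, we conclude that seliciclib is promising in the treatment of ACTH-producing pituitary tumors".

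Section 7.0 (Assessment of Efficacy) names a different primary set: patients whose baseline mean UFC (three specimens) is 1.5 times above the upper normal range and "who completed the 4-cycle, 4-week treatment period with no more than 2 weeks of interrupted drug doses". Its responder definition is a post-treatment mean UFC in the normal range. It does not cover missing specimens.

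Several rules can end treatment before week 4:

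- Section 5.0, Withdrawal of Subjects, stops drug in "those with toxicity greater than or equal to Grade 4 on the NCI-CTCAE"; Table 2 in Section 8.0 agrees.
- Section 8.0, Dose delays and dose reductions, addresses "a delay of more than 2 weeks for unresolved toxicity, but in general, such subjects should be withdrawn from the study".
- Table 4 (liver criteria): "Immediately and permanently discontinue IP".
- Glucose metabolism adverse events: patients with "fasting blood glucose values consistently as high as or above 240 mg/dL in spite of appropriate therapeutic interventions are discontinued from the study".
- Electrolyte metabolism adverse events: potassium persistently below 3.0 mmol/L despite treatment.

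The text after Table 3 gives permanent stoppers a completion evaluation on the day of their last dose. It does not say whether UFC is collected then, or whether such a patient is a responder, a non-responder or excluded.

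Section 4.0 (Study Design) gives the purpose: to "look for a sufficient effect of the drug on normalizing urinary free cortisol before proceeding to a larger, randomized placebo controlled trial".

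**The concern.** The rule and the analysis population cannot both be followed as written. If all 16 enrolled are the denominator, the Section 7.0 population has no stated role in the primary test. If the Section 7.0 population is primary, its size may not be 16.

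A patient who stops for toxicity or uncontrolled disease without normalizing is a treatment failure. Under Section 7.0 that patient is removed instead of counted. The glucose and potassium exits may be related to outcome. Section 2.0 says hypercortisolism predisposes to diabetes, and Section 8.0 says "High levels of cortisol also exert mineralcorticoid (aldosterone) activity, stimulating absorption of sodium and excretion of potassium at the renal collecting tubules". Patients leaving by those routes may be ones whose cortisol stayed high.

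At stake is the response rate, with its lower bound, that would be reported from a trial meant to inform a larger one. In an open-label study the denominator should not remain open until the results are known.

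**Working it through.** **1. The plan's own design.** Inputs from Section 9.0: n = 16, cut r = 3, p0 = 0.05, p1 = 0.25, X binomial.

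- Type I error = P(X ≥ 3 | 16, 0.05) = 1 − (0.4401 + 0.3706 + 0.1463) = 0.0429.
- Power = P(X ≥ 3 | 16, 0.25) = 1 − (0.0100 + 0.0535 + 0.1336) = 0.8029.

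The stated design reproduces. 16 is the smallest n that meets both limits, and power exceeds 80% by 0.3 points.

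**2. Effect on the reported rate.** Take three responders and remove k early-stopping non-responders. The rate is 3/(16 − k), a relative rise of 16/(16 − k). The lower bound is the exact (Clopper-Pearson) one-sided 95% limit.

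| k removed | Rate | Relative rise | Lower bound |
|---|---|---|---|
| 0 | 3/16 = 18.8% | none | 5.3% |
| 1 | 3/15 = 20.0% | 7% | 5.7% |
| 2 | 3/14 = 21.4% | 14% | 6.1% |
| 3 | 3/13 = 23.1% | 23% | 6.6% |
| 4 | 3/12 = 25.0% | 33% | 7.2% |

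The exact two-sided 95% interval for 3/16 is 4.0% to 45.6%. Four exits would turn 3 of 16 into the design's own promising rate. The documents give no drop-out rate, so k is a range and not a forecast.

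**3. Effect on the decision.** Removing a non-responder cannot raise a count of responders. With the cut held at 3, P(X ≥ 3 | n, 0.05) is 0.0429, 0.0362, 0.0301, 0.0245 and 0.0196 for n = 16, 15, 14, 13 and 12, so type I error falls. Re-deriving the cut for the smaller set changes nothing: the smallest cut with type I error at or below 0.05 is 3 for every n from 8 to 16.

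The decision can differ only if a responder lies outside the Section 7.0 set. One route exists on paper. Section 5.0 admits patients on two screening UFCs at least 1.5 times the upper limit. It also defines recurrent or persistent disease by UFC above the upper limit, without saying whether 1.5 times applies there too. Section 7.0 then filters on three later specimens. A dosed patient whose baseline mean falls below 1.5 times, and who normalizes, counts under Section 9.0 but not under Section 7.0. With exactly three responders, that is 3 on one reading and 2 on the other.

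**4. Effect on power.** If 25% is the rate among completers and exactly 1, 2 or 3 of the 16 are not evaluable, P(X ≥ 3 | 16 − k, 0.25) = 76.4%, 71.9% or 66.7%. If 25% is the rate among all treated patients, power stays 80.3%.

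**5. Which UFC is the endpoint.** Section 4.0 places the primary endpoint at week 4. Section 6.0 schedules collections on days 24–28 and again on days 30–35, with a completion visit on Day 36. Section 7.0 places the post-treatment specimens in the 5 days before study completion, which can be read as either collection. The scheduled end-of-study MRI and visual fields fall on Day 29, and Section 8.0 withdraws patients for tumor growth or worsening fields. A Day 29 withdrawal comes after the first collection but before the second, so whether it creates a missing endpoint depends on which one is primary.

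**The case against.** Section 9.0 speaks of enrolling 16 and then of 3 of the 16, so its natural reading is everyone enrolled. Section 7.0 defines a responder as someone who achieves a normal mean, and a patient with no result has not achieved it. Together these come close to the rule asked for. That stands, but it leaves the conflict with a population Section 7.0 itself calls primary, and the treatment of missing specimens remains an inference.

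The disease-linked exits are also limited. Section 5.0 excludes HbA1C above 8% and potassium below 3.5 on replacement, and Section 6.0 excludes severe metabolic complications. The glucose and potassium exits apply only after treatment has failed. Section 8.0 puts the disease's mild hypokalemia at 3.0–3.5 mmol/L, not below the exit threshold. Drug holds of up to 2 weeks stay in the set. The documents do not tie Grade 4 or liver exits to non-response, and a responder who exits would bias the rate downward. All this stands and makes many selective exits unlikely. It does not make them impossible.

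A reader might infer that the completer set makes a false promising verdict more likely. The documents do not support that: step 3 shows the opposite. Inflation would need replacement of drop-outs, over-enrolment or a lower cut, and the plan provides for none of these. A reader might also infer that the next trial would be undersized. The plan specifies no rate estimate or interval, and does not say the next trial will be sized on this rate, so that rests on assumptions outside the documents.

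**Conclusion.** The point holds as an unresolved conflict that should be fixed before analysis. It is not an error in the sample size. Sections 7.0 and 9.0 name different sets, and a missing end-of-treatment UFC has no status.

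Upward bias in the rate needs three things: computation on the Section 7.0 set, at least one responder, and at least one early-stopping non-responder. One or two exits are minor beside the sampling uncertainty; four would matter. The go decision is unaffected unless a responder falls outside the Section 7.0 set, most plausibly through the baseline filter. The power shortfall is modest but real if the 25% was meant for completers, because the design has almost no slack.

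**What to change.** In Sections 7.0 and 9.0:

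- Make the primary analysis all patients who receive at least one dose, and state that these are the 16.
- Count early stoppers and patients without the end-of-treatment UFC as non-responders, and judge 3 responders against 16.
- Report the present Section 7.0 completer set as a sensitivity analysis.
- State whether 25% is the rate among all treated patients (power 80.3%) or among completers (lower, as in step 4). The new wording does not restore that power.
- Name the primary UFC collection, days 24–28 or days 30–35, and bring Sections 4.0, 6.0 and 7.0 into line.

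Separately, reconcile the Section 5.0 entry criteria with the Section 7.0 baseline filter, and report results with and without that filter. Without it, a patient whose baseline mean is near normal could count as a responder.

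The cost is wording, with no added patients or visits. The reported rate or stated power may look slightly less favourable, and a patient who normalized but stopped early will count as a non-responder.

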### *Primary outcome:*

- The primary efficacy outcome will be normalization of mean UFC levels after 4-weeks treatment. This will be measured as the mean of three 24-hour urine specimens collected at baseline and within 5 days before completion of the study. Patients who achieve a mean post-treatment UFC level within the normal range are considered responders.

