**Primary endpoint:**

- A normalized urinary free cortisol level at week 4

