**Secondary endpoint:**

- A urinary free cortisol level above the upper limit of the normal range but reduced by  $\geq 50\%$  from baseline at week 4
- Plasma ACTH [ ] hour urinary free cortisol, serum and salivary cortisol levels over time
- Hemoglobin A1C (HbA1C), fasting blood glucose and blood electrolytes, e.g. K+
- Cushing's syndrome clinical signs and symptoms, e.g. weight, body mass index, blood pressure
- Changes in tumor size
- Safety end points: hematologic and blood chemistry including total sodium, potassium, urea, serum creatinine, creatinine clearance, total protein; LFT (ALT, AST, total bilirubin, albumin, ALP, [ ] total cholesterol (TC), LDL-cholesterol, triglycerides; coagulation (PT, INR) and ECG [ ]

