- Plasma ACTH and serum cortisol levels (every three hours from 9:00 – 15:00)
  - Blood draw will be done via intravenous catheter every 3 hours from 9AM to 3PM.
    - In the case that an intravenous catheter cannot be placed, one blood draw will be performed at every 3 hour interval.

- ECG
- 24 hour urinary free cortisol any time between days 24-28
  - Subjects will collect 3 - 24 hour UFC any time between days 24-28 prior to coming in for study visit 6
- 2 - late night salivary cortisol at 23:00-24:00 between days 24-28

Visit 6: Day #29

- History and physical exam
- Adverse events assessment
- CBC with differential, CMP (including fasting blood glucose), , PT/INR
- Fasting lipid profile, HbA1C
- Hormone profile: PRL, TSH, adjusted T4, free T4, IGF-1, LH, FSH, estradiol for females, testosterone (total and free) for males
- Serum Pregnancy Test (for females of childbearing potential)
- Plasma ACTH and serum cortisol levels (every three hours from 9:00 – 15:00)
  - Blood draw will be done via intravenous catheter every 3 hours from 9AM to 3PM.
    - In the case that an intravenous catheter cannot be placed, one blood draw will be performed at every 3 hour interval.
- ECG
- Visual Fields
- Pituitary MRI
- 24 hour urinary free cortisol on days any time between 30-35
  - Subjects will collect 3 - 24 hour UFC any time between days 30-35 prior to coming in for study completion visit
- 2 - late night salivary cortisol at 23:00-24:00 between days 30-35

Study Completion Visit: Day 36

- History and physical exam
- Adverse events assessment

Table 1. Study procedure flow sheet

Procedures	Screening Visit -60 to -1	Visit 1 Baseline	Visit 2 Day 1	Visit 3 Day 8	Visit 4 Day 15	Visit 5 Day 22	Visit 6 Day 29	Study Completion Visit
Standard of Care Procedures: Items, drugs and services that are part of regular care and would be done even if you did not take part in this research study. These will be billed to you and/or your insurance company.								
Visual Field Exam	X 							
MRI of the Pituitary	X 							
Research Related Procedures: Items, drugs and services done for research purposes only. These will be covered by the sponsor of the study and will NOT be billed to your insurance company.								
Review of medical records	X							
History and Physical Exam	X	X	X	X	X	X	X	X
Serum Pregnancy Test (for female of childbearing potential)	X	X	X	X	X	X	X	X

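### The rule that measures the primary outcome does not say which of two scheduled urine sets decides response: Days 24-28 (week 4) or Days 30-35 (before the Day 36 completion visit)

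*Combined protocol and SAP*

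**What the plan says.** Section 4.0, Primary endpoint, reads "A normalized urinary free cortisol level at week 4". The first secondary endpoint there, a partial reduction in urinary free cortisol (UFC), is also taken "from baseline at week 4".

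Section 7.0, Primary outcome, speaks of "normalization of mean UFC levels after 4-weeks treatment", then gives the measuring rule: "This will be measured as the mean of three 24-hour urine specimens collected at baseline and within 5 days before completion of the study". It adds: "Patients who achieve a mean post-treatment UFC level within the normal range are considered responders".

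Section 6.0 schedules two late sets of three specimens:
- Under Visit 5 (Day 22): "Subjects will collect 3 - 24 hour UFC any time between days 24-28 prior to coming in for study visit 6". Visit 6 is Day 29.
- Under Visit 6 (Day 29): "Subjects will collect 3 - 24 hour UFC any time between days 30-35 prior to coming in for study completion visit". The next entry is "Study Completion Visit: Day 36".

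Table 1, footnote 5, gives a different window for on-study collections: the 3 days before the visit. Section 9.0 declares the drug promising if at least 3 of 16 patients respond.

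**The concern.** Two analysts could each follow the protocol and score different urine. One starts from the Section 4.0 endpoint and takes Days 24-28. The other starts from the Section 7.0 rule, finds only one visit named for study completion, and takes Days 30-35. The sets need not agree, because the second falls after the last planned dosing week.

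This outcome alone drives the conclusion, and the cut-off is small, so a single patient can decide it. The trial is open-label and both sets of results will be in hand, so leaving the set unnamed also leaves room to choose one after seeing the data.

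**Working it through.** **1. The plan's own design figures.** Inputs from Section 9.0: n = 16, success at 3 or more responders, null rate 5%, target rate 25%, one-sided 0.05, 80% power. With X ~ Binomial(16, p):
- P(X ≥ 3 | p = 0.05) = 0.0429
- P(X ≥ 3 | p = 0.25) = 0.8029

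The design reproduces. The problem is one of definition, not of sample size.

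**2. Which set does the text point to?**

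| Cue | Place | Points to |
|---|---|---|
| Endpoint at week 4 | Section 4.0, primary and secondary endpoints | Days 24-28 |
| Five-day window | Section 7.0 | Five days before Day 29 are Days 24-28, an exact fit. Five days before Day 36 are Days 31-35, so Day 30 of the later set falls outside |
| End of study used for the last visual field exam, scheduled on Day 29 | Section 7.0, Secondary outcome; Section 6.0, Visit 6 | Days 24-28 |
| Completion of the study used of the 4-week treatment and preparation period | Section 4.0, Intervention | Days 24-28 |
| Study period described as 4 weeks | Section 11.0 | Days 24-28 |
| Completion of the study in the measuring rule; only the Day 36 visit carries that name | Section 7.0; Section 6.0 | Days 30-35 |
| After four weeks of treatment; post-treatment | Section 7.0 | Weak for either set; Section 9.0 uses post-treatment in a generic before-and-after sense |
| Three days before the visit | Table 1, footnote 5 | Days 26-28 or Days 33-35; matches neither Section 6.0 window |

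**3. Relation to dosing.** Dosing is on 4 days of each week for 4 weeks, and the documents do not say which days. Assume four consecutive days within Days 22-28 and no delay:

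| First dosing day of week 4 | Last dosing day | Dosing days within 24-28 | Dosing days within 30-35 | Days from last dose to Day 30 |
|---|---|---|---|---|
| 22 | 25 | 2 | 0 | 5 |
| 23 | 26 | 3 | 0 | 4 |
| 24 | 27 | 4 | 0 | 3 |
| 25 | 28 | 4 | 0 | 2 |

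**4. Exposure of the decision to one patient.** One reclassified patient changes the conclusion only when the count is 2 (a gain) or 3 (a loss). At p = 0.25:
- P(X = 2) = 120 × 0.25² × 0.75¹⁴ = 0.1336
- P(X = 3) = 560 × 0.25³ × 0.75¹³ = 0.2079
- Sum = 0.342

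**5. Ranges under assumption.** The documents give no figure for agreement between the two sets.

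(a) Suppose 25% respond on Days 24-28, a fraction f of them are no longer normal on Days 30-35, and nobody gains. The later rate is 0.25 × (1 − f). Later responders are then a subset of the earlier ones, so the chance of opposite decisions is 0.8029 minus the later power.

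| f | Later rate | Power on Days 30-35 | Opposite decisions |
|---|---|---|---|
| 10% | 0.225 | 73.3% | 7.0% |
| 20% | 0.200 | 64.8% | 15.5% |
| 50% | 0.125 | 32.3% | 48.0% |

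(b) Suppose the true rate is 5% on each set and the better set is chosen after seeing both. Let c be the chance that a responder on one set also responds on the other. Per patient, P(both) = 0.05c and P(first only) = P(second only) = 0.05(1 − c). Summing over 16 patients gives P(at least one set has 3 or more responders):

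| c | False-positive rate |
|---|---|
| 1 | 4.3% |
| 0.9 | 5.2% |
| 0.8 | 6.0% |
| 0.5 | 7.4% |
| 0.05 (unrelated) | 8.4% |

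**The case against.** The strongest reply is that the intended set is already clear. Several cues agree on Days 24-28, the five-day window fits that set exactly and the other only in part, and the protocol elsewhere uses study completion loosely for the 4-week period. Against this stands essentially one phrase. The trial is also an exploratory proof of concept with a laboratory endpoint, and the design figures are unaffected. All of that is fair, and it is why Days 24-28 is the natural choice. It does not remove the defect, because the phrase sits in the only sentence that says how the outcome is measured.

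Three stronger readings are tempting and are not supported:
- **That the plan scores response off drug, against an on-drug alternative.** Days 30-35 is one reading of the rule, not its plain meaning. Nor is the contrast clean: three days of every week are off-dose, and if the last dosing day is Day 25, all three earlier specimens could fall on Days 26-28.
- **That the 3-day scheduling tolerance makes the sets overlap.** The planned windows could stretch into each other on the calendar. Within a patient, however, Visit 6 separates them: the first set is collected before it and the second is listed under it.
- **That a treatment delay pushes the last dosing week past all urine collection.** This needs missed doses to be made up, which no section provides for. How visits follow delays is a separate question.

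It is also true that the ranges in step 5 are assumptions. The losses of 10% to 50% are illustrative. The false-positive figures require deliberate selection, and 8.4% requires unrelated sets in the same patients about a week apart.

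**Conclusion.** The concern holds as an inconsistency in the definition of the primary endpoint. Two scheduled sets can satisfy parts of the text, neither is named, and the measuring rule uses the name of the visit that most other cues do not support.

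The only size that rests on the plan's own design values is the 34.2% chance, at a true 25% rate, of a count at which one patient decides the result. It bounds exposure to a one-patient reversal from above. The chance of an actual reversal depends on agreement between the sets, which is unknown. As assumed ranges only, power on the later set could be 73.3% to 32.3% against 80.3%, and choosing the better set could give a false-positive rate of 5.2% to 8.4% against 4.3%.

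This should be corrected before results are seen, because a set chosen afterwards cannot be shown to be free of the data.

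**What to change.** Before any on-treatment UFC data are reviewed, reconcile the Section 4.0 endpoints, the Section 6.0 schedule, Table 1 footnote 5 and the Section 7.0 primary outcome by naming one set as primary.

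- The set most consistent with the text is the mean of the three 24-hour specimens collected after Visit 5 and before Visit 6 (planned Days 24-28).
- In Section 7.0, put that wording in place of the reference to the five days before study completion and in place of the post-treatment label in the responder definition.
- Align Table 1 footnote 5 with the Section 6.0 collection windows.
- Report the Days 30-35 set separately, labelled as supportive.

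The cost is a wording amendment. Both sets are already scheduled, so no collection is added, and n = 16 and the cut-off of 3 are unchanged.
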